1.0 List of Abbreviations

Abbreviation	Term
AE	Adverse Event
BPI	Brief Pain Inventory
CRF	Case Report Form
EOT	End of Treatment
INR	International Normalized Ratio
ITT	Intent to Treat
NMES	Neuromuscular Electrical Stimulation
OA	Osteoarthritis
PCS	Pain Catastrophizing Scale
PGIC	Patient Global Impression of Change
PNS	Peripheral Nerve Stimulation
POD	Post-Operative Day
PP	Per Protocol
QoL	Quality of Life
RCT	Randomized Controlled Trial
SOC	Standard of Care
TENS	Transcutaneous Electrical Nerve Stimulation
TKA	Total Knee Arthroplasty
TUG Test	Timed Up and Go Test
WOMAC	Western Ontario and McMaster Universities Arthritis Index

2.0 Protocol Synopsis

Title	A Prospective, Comparative Effectiveness Randomized Controlled Trial of SPR peripheral nerve stimulation (PNS) therapy for the treatment of pain following total knee arthroplasty (TKA) utilizing preoperative lead placement
Investigational (Test) Device	SPRINT® Beta Peripheral Nerve Stimulation (PNS) System [REDACTED]
Study Design	Prospective, Comparative Effectiveness Randomized Controlled Trial
Primary Study Objective	To determine if the addition of PNS therapy to the site's standard of care for treatment of knee pain following TKA is significantly different than that of the site's standard of care alone.
Study Plan	
Individuals undergoing a primary unilateral TKA will be considered for enrollment into the study. After obtaining informed consent, potential subjects will be evaluated for general eligibility.
 
Qualifying subjects will be randomized to either Group #1 (Treatment) or Group #2 (Control). All subjects will receive the site's standard of care (SOC) for the treatment of knee pain before, during, and after the TKA. Subjects assigned to Group #1 will also receive Peripheral Nerve Stimulation Therapy for up to approximately 30 days before the procedure, and again starting immediately after the TKA for a total of up to 60 days.
 
[REDACTED]
 
[REDACTED]
 
Subjects will receive treatment [REDACTED] for 4 weeks post-TKA. At the conclusion of the treatment period, the leads will be removed.
 
Subjects in both groups will receive the site's SOC for treatment of knee pain before, during and after TKA. Subjects will complete a daily diary recording their medication usage and daily [REDACTED] Pain [REDACTED]. Other outcomes that will be assessed include tests of function, stimulation characteristics, surveys/questionnaires, pain scores and pain treatments.
 
Outcomes will be assessed based on the schedule of study procedures (Appendix A).

Sites (N)	Up to 10 investigational sites
Subjects (N)	Approximately 50 subjects will be enrolled. Subjects will be randomized to either Group #1 (Treatment) or Group #2 (Control).
Inclusion Criteria	
 • Between the age of 21 and 90 years old • Scheduled to undergo a primary unilateral total knee replacement procedure • Able to understand and provide written consent • Able to comply with all study requirements (e.g., if needed, has a caregiver to assist)
Exclusion Criteria	
 • Body Mass Index (BMI) > 40 kg/m² • Conditions that place the subject at increased risk of infection in the opinion of the investigator, [REDACTED] • History of valvular heart disease • Implanted cardiac pacemaker/defibrillator or Deep Brain Stimulator • Bleeding disorder OR INR ≥ 1.5 for those on warfarin (Group #1, only) • Confounding conditions [REDACTED] [REDACTED] or central nervous system disorders • History of nerve damage [REDACTED] • Allergy to skin surface electrodes and/or medical-grade adhesive tapes • Contraindications to the proposed anesthetic protocol during lead placement [REDACTED] • Any other medical condition that may interfere with ability to participate in a clinical trial as determined by the Investigator • Prisoners, minors or individuals that report to investigators (e.g., students, employees) • Pregnant (Group #1, only) • History of substance abuse within 6 months • Potential secondary gain issues (e.g., pending claims or receiving disability)
Primary Safety Endpoint	Occurrence of device-related adverse events.
Primary Clinical Endpoint	
The primary clinical endpoint is average daily pain while walking. Subjects will record [REDACTED] pain while walking [REDACTED] in a daily diary [REDACTED]
 
[REDACTED] The difference in the [REDACTED] pain scores between the two groups (Treatment vs. Control) will be calculated to determine if PNS Therapy provides a [REDACTED] reduction in [REDACTED] daily pain while walking.

Secondary Endpoints	Pain-related outcomes

	
 • Pain intensity over the last 24 hours as recorded as Average pain [REDACTED] • Pain intensity [REDACTED] • Pain right now [REDACTED] • Cumulative analgesic usage [REDACTED] • Opioid-related side effects [REDACTED] 
Functional outcomes
 
 • Timed Up and Go [REDACTED] • 6 minute walk test [REDACTED] • Change in pain, physical function, and stiffness [REDACTED] • Patient Global Impression of Change (PGIC) [REDACTED] • Pain Catastrophizing Scale (PCS) [REDACTED] • Time to meet recovery milestones [REDACTED] • [REDACTED] 
Subject Satisfaction Survey
 
 • Inpatient Pain Management Experience Survey [REDACTED] • Compliance [REDACTED] • [REDACTED] 
Physical Therapy Sessions

Exploratory Measurements	
 • [REDACTED] primary and secondary endpoints at study intervals not specified • Pain coverage [REDACTED] • [REDACTED] sensation coverage of leg [REDACTED] • Clinician Satisfaction Survey [REDACTED]
Key Demographic Information	
 • Body Mass Index (BMI) [REDACTED] • Surgical approach [REDACTED] • Use of post-operative drains [REDACTED] • [REDACTED] knee implant used [REDACTED]

3.0 General Information

3.1 Title of Investigation

A Prospective, Comparative Effectiveness Randomized Controlled Trial of SPR peripheral nerve stimulation (PNS) therapy for the treatment of pain following total knee arthroplasty (TKA) utilizing preoperative lead placement

3.3 Study Materials

The SPRINT® Beta Peripheral Nerve Stimulation (PNS) System:

[figure not shown]
3.4 Study Objective

To compare the effectiveness and safety of PNS therapy in conjunction with the SOC to SOC alone for the treatment of knee pain following TKA.

4.0 Introduction and background

4.1 Introduction

The goal of this research is to gather data regarding the safety and effectiveness of PNS therapy for the treatment of pain following total knee arthroplasty (TKA; a.k.a. total knee replacement).

stimulation will [REDACTED] produce greater pain relief than with standard of care alone.

4.2 *Background*

Postoperative pain following total knee arthroplasty is a substantial medical problem

Present treatments for postoperative TKA pain are ineffective, carry risks of side effects/complications, and/or are not indicated for extended use.

[figure not shown]
The proposed non-narcotic therapy may reduce postoperative pain with minimal risk of infection and falls

The proposed method aims to relieve postoperative pain following TKA by delivering electrical stimulation through percutaneous [REDACTED] SPRINT MicroLeads

The proposed therapy may provide immediate pain relief following TKA that can be delivered for several weeks as patients continue their postsurgical recovery

The proposed method may provide immediate pain relief [REDACTED]

The proposed method has been [REDACTED] used to [REDACTED]
[REDACTED] reduce chronic pain in patients with lower limb amputations

The proposed method to treat postoperative pain following TKA has been tested as a treatment for chronic pain in individuals with lower limb amputations [REDACTED]

Electrical stimulation was delivered through [REDACTED] leads [REDACTED]

The proposed method has been tested to treat pain in patients following TKA in separate preliminary studies.

[REDACTED]

Summary

[REDACTED]

The proposed study will determine if this therapy in combination with the site's respective SOC can produce significant reductions in postoperative pain following TKA as compared to the site's SOC alone.

5.0 Study Outcomes and Exploratory Measures

5.1 Overview

In both groups, outcomes and exploratory measures will be collected before and after TKA surgery (see Appendix A for schedule of study procedures) and include

1. Average Pain while walking, at rest, and average over the last 24 hours [REDACTED]
2. Pain right now [REDACTED]
3. Cumulative analgesic usage [REDACTED]
4. Opioid-related side effects [REDACTED]
5. Timed Up and Go [REDACTED]
6. Six Minute Walk Test [REDACTED]
7. [REDACTED]
8. Patient Global Impression of Change (PGIC)
9. Pain Catastrophizing Scale (PCS)
10. Time to meet recovery milestones
11. Subject satisfaction survey
12. Inpatient Pain Management Experience Survey
13. Pain Distribution
14. [REDACTED] sensation [REDACTED]
15. Clinician satisfaction survey
16. Compliance [REDACTED]
17. [REDACTED] Physical Therapy Sessions

5.2 Primary Outcome

The primary outcome of this study will be the average daily pain while walking over the first 4 weeks following TKA surgery.

5.3 Secondary Outcomes

Secondary outcome measures will provide additional information on pain and function.

The [REDACTED] is a widely used assessment designed to measure pain intensity and the interference of pain on daily activities and moods [REDACTED]

Cumulative Analgesic usage

The amount and type of analgesic used by the subject will be recorded daily in a diary before TKA surgery, from the subject's records during their hospital stay, in daily diaries after discharge from the hospital, and at each visit following End of Treatment.

Opioid-related Side Effects

Opioid pain medications are associated with a wide variety of side effects. Common side effects include nausea and vomiting, constipation, urinary retention, pruritus, drowsiness, and respiratory depression.

Timed Up and Go [REDACTED]

The [REDACTED] is an objective measure of mobility. [REDACTED]

Six minute walk test [REDACTED]

The [REDACTED] records the total distance the subject can walk in 6 minutes. [REDACTED]

The [REDACTED] is a widely-used validated questionnaire to evaluate patients with osteoarthritis of the knee and consists of 24 items evaluating pain (5 items), stiffness (2 items), and physical functional disability (17 items) [REDACTED]

Patient Global Impression of Change (PGIC)

Participant ratings of global improvement are one of the core outcome domains in chronic pain studies (Dworkin *et al.* 2005). [REDACTED]

Pain Catastrophizing Scale (PCS)

The PCS is a widely-used, validated and reliable 13-question instrument to assess rumination (4 questions), magnification (3 questions), and helplessness (6 questions) (Sullivan, 2009.; Osman *et al.* 1997). [REDACTED]

Time to Meet Recovery Milestones

The time until the subject meets criteria related to hospital discharge will be measured. [REDACTED]

Subject Satisfaction Survey

A survey will be administered to assess subject satisfaction with the study and postsurgical pain therapies.

Inpatient Pain Management Experience Survey

This survey is comprised of a subset of questions from the Hospital Consumer Assessment of Healthcare Providers and Systems. This survey will be administered to assess subject satisfaction with pain management during their time in the hospital for TKA surgery.

Compliance

SPRINT Beta stimulator [REDACTED]

[REDACTED] subject compliance [REDACTED]

Physical Therapy Sessions

[REDACTED] physical therapy sessions

5.4 Exploratory Measures

[REDACTED] primary and secondary endpoints at other study intervals

The primary and secondary endpoints [REDACTED] at other study intervals not listed above.

Pain Distribution

Subjects will be asked where they are experiencing pain in the lower limbs.

[REDACTED] sensation coverage [REDACTED]

[REDACTED] comfortable sensations.

Clinician satisfaction survey

A sponsor-developed Clinician Satisfaction Survey will be administered. [REDACTED]

5.5 Safety Endpoint

The primary safety endpoint is the occurrence of protocol-related adverse events.

6.0 Device Description

6.1 Overview

This study utilizes the SPRINT® Beta PNS System.

SPR Therapeutics, Inc.

CONFIDENTIAL

Page 19 of 63

SPR Therapeutics, Inc.

CONFIDENTIAL

Page 20 of 63

A horizontal bar chart consisting of 10 bars. The bars are black with white outlines. The lengths of the bars decrease from left to right. The first bar is the longest, followed by a short bar, then a long bar, then a short bar, then a long bar, then a short bar, then a long bar, then a short bar, then a long bar, and finally a very short bar.

A large black rectangular redaction box covers the majority of the page content, from approximately y=113 to y=250. The redaction is composed of three horizontal bars: a top bar from x=160 to x=830, a middle bar from x=10 to x=220, and a bottom bar from x=10 to x=990.

ANSWER

ANSWER

© 2013 Pearson Education, Inc.

ANSWER

Digitized by [contact]

11. **What is the primary purpose of the *Journal of Clinical Endocrinology and Metabolism*?**

For more information, contact the Office of the Vice President for Research and Economic Development at [contact] or www.iowa.edu/research/.

© 2000 by the author

Digitized by [contact]

[REDACTED]

[REDACTED]

[REDACTED]

[REDACTED]

[REDACTED]

[REDACTED]

[REDACTED]

7.0 Study Scope

7.1 Number of Sites

Up to 10 investigational sites.

7.2 Number of Subjects

Up to 50 subjects will be enrolled in this study. All subjects will receive the site's SOC for the treatment of knee pain before, during and following TKA. Subjects assigned to Group #1 will also receive PNS Therapy before and after TKA. All subjects who sign an informed consent form will receive a subject ID number. Qualifying subjects will be randomized to either Group #1 (Treatment) or Group #2 (Control).

[REDACTED]

[REDACTED]

[REDACTED]

8.0 Study Protocol

8.1 Overview

This study is a prospective randomized controlled trial to determine if the treatment effect of PNS therapy plus each site's standard of care (SOC) for treatment of knee pain following total knee arthroplasty (TKA) is significantly different than that of the site's SOC alone.

8.2 Study Population

Prospective subjects will be screened for eligibility into the study from the available pool of candidates who are scheduled to undergo a primary unilateral TKA. Subjects will be screened using the Eligibility criteria listed in section 8.3. Recruitment materials will be provided to aid in subject enrollment. All recruitment materials will be IRB approved prior to their use.

8.3 Eligibility

8.3.1 Inclusion Criteria

1. Between the age of 21 and 90 years old
2. Scheduled to undergo a primary unilateral total knee replacement procedure
3. Able to understand and provide written consent
4. Able to comply with all study requirements (e.g., if needed, has a caregiver to assist)

8.3.2 Exclusion Criteria

1. Body Mass Index (BMI) $> 40 \text{ kg/m}^2$
2. Conditions that place the subject at increased risk of infection in the opinion of the investigator, [REDACTED]
[REDACTED]
[REDACTED]
3. History of valvular heart disease
4. Implanted cardiac pacemaker/defibrillator or Deep Brain Stimulator
5. Bleeding disorder OR INR ≥ 1.5 for those on warfarin (Group #1, only)
6. Confounding conditions [REDACTED]
[REDACTED] or
central nervous system disorders
7. History of nerve damage [REDACTED]
8. Allergy to skin surface electrodes and/or medical-grade adhesive tapes
9. Contraindications to the proposed anesthetic protocol [REDACTED]
10. Any other medical condition that may interfere with ability to participate in a clinical trial as determined by the Investigator
11. Prisoners, minors, or individuals that report to investigators (e.g., students, employees)
12. Pregnant (Group #1, only)
13. History of substance abuse within 6 months
14. Potential secondary gain issues (e.g., pending claims or receiving disability)

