8.5.1 Visit 1: Consent and Randomization

Subjects will receive a detailed explanation of study-specific procedures as well as the risks and benefits of participating in the study. The subject will be asked to sign the approved study consent during this visit. If the subject agrees to participate by signing the consent form, all inclusion/exclusion criteria will be verified by completing the eligibility form and then all baseline information and outcome measurements will be collected and recorded on the appropriate case report form (CRF) in accordance with the schedule of study procedures (see Appendix A).

Subjects will receive a one-week daily diary to be completed prior to Visit 2.

8.5.2 Visit 2: Lead Placement Visit (Group #1 only) and Check-in Call (Both Groups)

[REDACTED]

[REDACTED]

[REDACTED]

[REDACTED]

[REDACTED]

[REDACTED]

[REDACTED]

[REDACTED] [REDACTED]

[REDACTED] [REDACTED]

[REDACTED]

[REDACTED]

[REDACTED]

[REDACTED]

[REDACTED]

[REDACTED]

[REDACTED]

[REDACTED]

[REDACTED]
[REDACTED]
At the conclusion of the Lead Placement Visit, subjects in Group #1 will either:

a. Proceed to treatment phase:

(i) Subjects with acceptable lead placement and stimulation parameters will be prepared to proceed to the treatment phase (See Below). These subjects will start completing a daily diary.

OR

b. Return for another Visit 2:

(i) If there is not sufficient time to complete lead placement or the testing, or if the subject does not respond to stimulation, the investigator may present the subject with the option to return for a repeat lead placement visit.
[REDACTED]

OR

c. Terminate from the Study:

[figure not shown]
(i) If the subject does not wish to continue with further lead placement or if an additional lead placement visit is needed [REDACTED], they will be terminated from the study if no adverse events (AE) are noted at the 24-48 hour telephone Check-In Call. If an AE is noted, the subject will be followed until the AE resolves.

Treatment Phase:

[REDACTED]

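### Exclusion items 5 and 12 apply to the randomised Treatment arm only, so eligibility as written depends on allocation and can remove a subject after randomisation from one arm

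*Combined protocol and SAP*

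**What the plan says.** Two exclusion criteria carry a group restriction, in both the synopsis (section 2.0) and section 8.3.2. Item 5 reads "Bleeding disorder OR INR ≥ 1.5 for those on warfarin (Group #1, only") and item 12 reads "Pregnant (Group #1, only"). Group #1 is the Treatment arm and is reached only by randomisation. Section 7.2 states: "Qualifying subjects will be randomized to either Group #1 (Treatment) or Group #2 (Control").

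The order of events is also stated. Section 8.2: "Subjects will be screened using the Eligibility criteria listed in section 8.3". Section 8.5.1, the consent and randomisation visit, says that after consent "all inclusion/exclusion criteria will be verified by completing the eligibility form". The same section adds: "Subjects will receive a one-week daily diary to be completed prior to Visit 2". Leads are placed at Visit 2, in Group #1 only.

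Three other places bear on the consequence:

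- Section 8.5.2 says that a Group #1 subject who does not want further lead placement, or who needs an additional placement visit under a partly redacted condition, is discontinued from the study. This applies if the check-in call at 24-48 hours shows no adverse event; otherwise the subject is followed until the event resolves.
- Section 10.2 aims for maximum retention and little missing data.
- Section 10.4 plans intent-to-treat (ITT) and per-protocol (PP) analyses of the primary and secondary endpoints. Both definitions are redacted.

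**The concern.** A criterion that applies to one randomised arm cannot decide who qualifies before the arm is known. INR, bleeding history and pregnancy can be recorded for everyone at Visit 1, but what follows from them depends on the allocation. The text therefore permits exclusion after randomisation in Treatment, with no counterpart in Control.

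What is at stake is the comparability of the arms for the primary comparison, average daily walking pain over the first 4 weeks after surgery. If subjects meeting item 5 or 12 drop out of Treatment but stay in Control, and their pain differs from that of other subjects, the difference between arms carries a selection component. That component does not shrink as the sample grows.

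The scope of item 5 also needs stating. The restriction comes at the end of a two-part criterion and could cover both parts or only the INR part, so sites could apply it differently.

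**Working it through.** **Can the passages all be followed?** Take a candidate on warfarin with an INR of 1.5 or more.

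1. At Visit 1 all criteria are verified (8.5.1) and only those who qualify are randomised (7.2).
2. Whether this candidate meets item 5 depends on the group (8.3.2), which is not yet assigned.
3. If the candidate is held to qualify and is then allocated to Control, nothing further happens. If allocated to Treatment, item 5 now excludes a randomised subject.
4. If the candidate is held not to qualify, the group restriction has no function.

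So either eligibility is settled before allocation or the group restriction has effect, but not both. No readable text resolves this.

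**How large could the effect be?** The plan gives no figure to reproduce: the readable text has no prevalence, SD or allocation ratio. From section 7.2, N is up to 50. Assumed: 1:1 allocation (25 per arm), a share f of 2%, 5% or 8% meeting item 5 or 12, a difference d of 0.5 or 1 SD in mean pain between those subjects and the rest, and a two-sided 5% test. No direction of bias is claimed.

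Expected affected Treatment subjects: 25f = 0.5, 1.25 or 2. Chance of at least one: 1 − (1 − f)^25 = 40%, 72% or 88%.

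*Case A: affected Treatment subjects are left out, like Control subjects stay.* Bias = f × d, and SE = √(1/(25(1 − f)) + 1/25) in SD units. Type I error comes from the noncentral t distribution with noncentrality bias/SE.

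| f | d (SD) | Bias (SD) | SE (SD) | Bias/SE | Type I error |
|---|---|---|---|---|---|
| 2% | 0.5 | 0.010 | 0.284 | 0.035 | 5.01% |
| 5% | 0.5 | 0.025 | 0.287 | 0.087 | 5.08% |
| 5% | 1 | 0.050 | 0.287 | 0.174 | 5.34% |
| 8% | 1 | 0.080 | 0.289 | 0.277 | 5.85% |

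At 33:17 or 17:33 (Treatment:Control) the maximum is 5.8%. Type I error reaches 10% only when about 20% of the arm (5 of 25) is removed at d = 1, or about 45% (11 of 25) at d = 0.5.

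*Case B: affected Treatment subjects are kept as randomised but receive no stimulation and no benefit from it.* There is no exclusion bias. The effect is multiplied by 1 − f = 0.98, 0.95 or 0.92. An effect of 0.81 SD gives 80% power at 25 per arm; power becomes 78%, 76% or 73%.

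*Screening cost of one common set of criteria.* 50/(1 − f) − 50 = 1.0, 2.6 or 4.3 more candidates.

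**The case against.** The strongest reply is that the harm depends on text that cannot be read. Bias needs affected Treatment subjects to leave follow-up or the analysis, and the readable text leans the other way: section 10.4 plans an ITT analysis and section 10.2 aims for retention. This stands. A reader might infer that the primary comparison is biased. The documents do not support that, because the handling of such subjects and the ITT and PP definitions are redacted, and a redaction is not a gap in the plan.

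A second reply is that the effect is negligible on the review's own numbers. That holds within the assumed range, but the documents give no basis for 2-8% or for 0.5-1 SD, so the break-even values are the safer guide.

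A third is that a closing parenthesis most naturally covers the whole of item 5. That is the likelier reading, so the request there is only for clarification.

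A reader might also infer that the list is inconsistent, because item 8, "Allergy to skin surface electrodes and/or medical-grade adhesive tapes", and item 9, on the anesthetic protocol, show no group restriction although they relate to the device or its placement. This does not hold. Item 9 is followed by a redaction that could contain one, and applying item 8 to both arms is exactly what is recommended here.

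None of these replies removes the contradiction between the group restriction and eligibility settled before randomisation.

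**Conclusion.** The point holds as a minor design matter. The readable text makes eligibility depend on allocation and permits one-sided exclusion after randomisation. Bias is conditional: if everyone is followed and analysed as randomised there is none from this source, only dilution of 2-8% under the Case B assumptions. If affected Treatment subjects are omitted, type I error is 5.0-5.9% with 25 per arm, 2-8% affected and 0.5-1 SD, all assumed, and it reaches 10% only at about 20% removed with a 1 SD difference.

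Two things keep it from being purely editorial. A common set of criteria changes who may enrol. And section 8.5.2 already contains a readable exit from the study that applies to Group #1 only, so departure from one arm after allocation is a real feature of the plan. Whether subjects who leave by that route remain in the ITT analysis cannot be determined.

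**What to change.** Reconcile the exclusion lists in sections 2.0 and 8.3.2 with sections 7.2, 8.2 and 8.5.1, so that one set of eligibility criteria is assessed identically in every candidate before allocation is revealed. Make the scope of item 5 explicit. The clinical content and thresholds are for the sponsor.

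A check before allocation does not close the matter, because at least a one-week diary separates Visit 1 from Visit 2 and a subject's status can change in that time. So also confirm, or state if the redacted text does not already do so, that every randomised subject stays in follow-up and in the as-randomised ITT analysis. This should cover Group #1 subjects later found to meet item 5 or 12, and those whom section 8.5.2 discontinues after lead placement fails or is declined.

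The cost is a change in two lists, at most a sentence or two on retention, and a sponsor decision on the eligible population. If the exclusions are applied to all candidates, about 1-4 more are screened to randomise 50 under the assumed 2-8%, and a few people who could have served only as controls (0.5-2 of 25) are not enrolled.
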